### CONFIDENTIAL

This document is confidential and the property of Stryker Orthopaedics. No part of it may be transmitted, reproduced, published or used by other persons without prior written authorization from Stryker.

Orthopaedics

Version	Description	Changed By
A 8/3/2007	New	[name]
B 9/12/2007	Statistical analysis and sample size are included. Knee and Osteoarthritis Outcome Score (KOOS) is added.	[name]
C 10/29/2007	Modified all study design parameters, including but not limited to primary and secondary objectives, reference therapies, inclusion/exclusion criteria, and evaluation tools.	[name]
D 12/3/2007	Basis of primary objective changed to Knee Society Score (KSS). Modified non-inferiority statistical analysis and sample size included. Additional patient questionnaire included. Joint line (JL) guidelines modified. Entire protocol revised. Appendices created.	[name]
1.0 3/3/2008	Draft status removed.	[name]
2.0 3/27/2013	Removed trademark and service marks per current Intellectual Property guidelines.	[name]

### **Protocol Change History**

CONFIDENTIAL

	Added clarification throughout that	
	only cases implanted with the	
	required study device will count	
	toward the enrollment goal.	
	Updated study devices and	
	description to remove the	
	unavailable Triathlon TS Extended	
	Condyle Femoral Component and	
	Triathlon TS Tibial Insert and	
	include N2Vac tibial inserts and	
	patellar components.	
	Added Appendix I.	
	Updated section 12.3 to remove	
	references to outdated	
	complication rate data.	
		1

## List of Abbreviations

ADE	Adverse Device Effect
AE	Adverse Event
ANCOVA	Analysis of Covariance
AP	Anteroposterior
BMI	Body Mass Index
CRF	Case Report Form
CSA	Clinical Study Associate
CSM	Clinical Study Manager
DCF	Data Clarification Form
EC	Ethics Committee
ECF	Extended Condyle Femur
FH	Fibular Head
GCP	Good Clinical Practice
HIPAA	Health Insurance Portability and Accountability Act
HSS	Hospital for Special Surgery
ICMJE	International Committee of Medical Journal Editors
IPP	Inferior Pole of the Patella
IRB	Institutional Review Board
JL	Joint Line
KOOS	Knee and Osteoarthritis Outcome Score
KSS	Knee Society Score
LEAS	Lower Extremity Activity Scale
ME	Medial Femoral Epicondyle
ML	Mediolateral
PER	Product Experience Report
PI	Primary Investigator
PMMA	Polymethylmethacrylate
PS	Posteriorly Stabilized
QOL	Quality of Life
ROM	Range of Motion
SAE	Serious Adverse Event
SC	Study Coordinator
SF-36	Short Form-36
TS	Total Stabilizer
TT	Tibial Tubercle
TKR	Total Knee Replacement
UADE	Unanticipated Adverse Device Effect
UHMWPE	Ultra High Molecular Weight Polyethylene

CONFIDENTIAL

# Study Synopsis

Title	A prospective, post-market, multi-center study of the outcomes of the	
	Triathlon TS Total Knee System	
Short Title	Triathlon TS Outcomes Study	
Protocol Number	65	
Phase	Post-market	
	This study will be a prospective, non-randomized evaluation of the	
Methodology	change between preoperative and postoperative outcomes for those	
	receiving the Triathlon TS Total Knee System.	
	Long term follow-up of each revision total knee replacement	
Study Duration	(TKR) case to 5 years	
	Anticipated enrollment period of 53 months	
	Approximate 10-year total duration	
Study Center(s)	12	
	The mean total KSS change is not 10% worse than, or is superior to,	
Hypothopia	the expected change according to published revision TKR data, for	
	cases implanted with the Triathlon TS Total Knee System as compared	
	from preoperative to 2 years postoperative.	

#### Page 1

### CONFIDENTIAL

	Primary:
	• To evaluate the change in outcomes from the preoperative time point to 2 years postoperative in cases implanted with the Triathlon TS Total Knee System, with regard to both components of the KSS.
	Secondary:
Objectives	
 
To evaluate the effect of JL restoration on postoperative stability, anterior knee pain and functional performance. A subset of revision TKR cases will be analyzed by comparing between two groups:
 

	
 
Cases with JL restoration > 5 mm and cases with JL restoration ≤ 5 mm
 

	
 
To evaluate the change between preoperative and postoperative outcomes other than the KSS for the Triathlon TS Total Knee System group.
 

	
 
To review radiographic stability, revision rates and complications for those implanted with the Triathlon TS Total Knee System.
 

Number of Subjects	181 cases implanted with the Triathlon TS Total Knee System as required under this protocol

	Inclusions:
	
 
A. Patient has signed an IRB approved, study specific Informed Patient Consent Form.
 
B. Patient is a male or non-pregnant female age 18 years or older at time of study device implantation.
 
C. Patient is a candidate for revision of all femoral and tibial components of a total knee replacement.
 
D. Patient is willing and able to comply with postoperative scheduled clinical and radiographic evaluations and
 

	rehabilitation.
Diagnosis and Main	Exclusions:
Inclusion/Exclusion	
Criteria	E. Patient has a Body Mass Index (BMI) > 40.
	F. Patient has an active or suspected latent infection in or about
	the affected knee joint at time of study device implantation.
	G. Patient has a neuromuscular or neurosensory deficiency, which
	limits the ability to evaluate the safety and efficacy of the device.
	H. Patient is diagnosed with a systemic disease (e.g. Lupus
	Erythematosus) or a metabolic disorder (e.g. Paget's Disease)
	leading to progressive bone deterioration.
	I. Patient is immunologically suppressed or receiving steroids in
	excess of normal physiological requirements (e.g. > 30 days).
	J. Patient has a failed unicondylar knee prosthesis.
	K. Patient has a known sensitivity to device materials.
	L. Patient is a prisoner.

	Triathlon TS Total Knee System
Study Device	
 
Required Components:
 
Triathlon TS Femoral Component
 
Triathlon TS Plus Tibial Insert or Triathlon PS Tibial Insert
 
Triathlon TS Universal Tibial Baseplate
 
 The femoral component and tibial baseplate must be used in a cemented application.
	The subject's patellar component may or may not be revised based
	must be used, and in a cemented application.
	Additionally, a variety of Triathlon TS device accessories may be used.
Reference Therapy	Comparison of preoperative to postoperative outcomes, both within the
	study group and with respect to published revision TKR data.

## Primary:

	A one-sided 95% confidence interval of the total KSS change from preoperative to 2 years postoperative (2 years - preoperative) will be computed at 2 years postoperative. For the non-inferiority comparison, the lower bound of this confidence interval will be compared with 63 points (10% worse than the expected improvement). For the superiority comparison, the lower bound of this confidence interval will be compared with 70 points (the expected improvement).
Statistical Methodology	Secondary:
	An independent group t-test or a nonparametric test will be used to
	compare the secondary numerical parameters (e.g. KSS, HSS, KOOS)
	between the JL restoration subgroups at 1, 2 and 5 years
	postoperative; and a Chi-square test or Fisher's exact test will be used
	to compare the secondary categorical parameters (e.g. postoperative
	stability, anterior knee pain and functional performance) between the
	subgroups. In addition, a paired t-test or Wilcoxon rank sum test will be
	used to compare the change in outcomes other than the KSS from
	preoperative to 1, 2 and 5 years postoperative within the Triathlon TS
	Total Knee System group. The radiographic stability rates, adverse
	event (AE) rates and revision rates with 95% confidence intervals will
	be presented in tables.

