#### CONFIDENTIAL

The protocol for measuring JL is referenced in Appendix A. Stability, anterior knee pain and the functional component of the KSS will be evaluated with respect to JL.

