### CONFIDENTIAL

### 2.1.2 Secondary

The secondary objectives of this study will be to evaluate the effect of JL restoration on revision TKR with specific reference to effect on postoperative stability, anterior knee pain and functional performance at 2 and 5 years postoperatively. It is expected that the Triathlon® TS group with JL elevation > 5 mm is non-inferior to the Triathlon TS group with JL elevation  $\leq$  5 mm.

All outcomes other than the change in KSS, already analyzed as the primary objective, will be analyzed from preoperative to 1, 2 and 5 years postoperatively.

Additionally, the long-term performance of the Triathlon TS Total Knee System for revision TKR will be evaluated with regard to radiographic stability, revision rate and complications when reviewed against published data.

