## 9.1.2 Secondary Efficacy Parameters

The secondary efficacy parameters will include:

- KSS pain and function score changes from preoperative at 1, 2 and 5-year visits
- SF-36 changes from preoperative at 1, 2 and 5-year visits
- KOOS changes from preoperative at 1, 2 and 5-year visits
- HSS Patella Score changes from preoperative at 1, 2 and 5-year visits
- LEAS score changes from preoperative at 1, 2 and 5-year visits

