## 9.1.5 Secondary Efficacy Analysis

A two-sided 0.05 alpha level will be used.

For the secondary efficacy parameters when data is available, comparisons of numerical variables between subgroups (e.g. JL groups) will be made by a paired t-test or Wilcoxon rank sum test; comparisons of categorical variables between subgroups will be made by a Fisher's exact test.

One-way analysis of covariance (ANCOVA) may be used as a supportive analysis to determine if the score change from preoperative is significantly different between the subgroups after adjusting the preoperative covariates (e.g. age, gender, BMI), if appropriate.

The mean score improvement from the preoperative time point within the Triathlon® TS Outcomes Study will be summarized in tables at each nominal visit. A p-value will be presented to determine if the mean score improvement from the preoperative time point is non-zero, if appropriate.

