## 9.4 Statistical Methodology

### 9.4.1 Data Summary

The following is a detailed proposal of statistical analyses planned for data collected during the study.

Descriptive statistics will be computed for all preoperative conditions and demographic parameters. That is, for continuous data (e.g. KSS) the N, mean, median, standard deviation, minimum and maximum will be computed. For categorical data (e.g. gender) the frequency will be computed. If appropriate, the data will be presented by appropriate subgroups (e.g. center).

Descriptive statistics and statistical comparisons for important demographic, efficacy and safety variables will be provided in tables.

Statistical analyses will use SAS® software version 9.1 or higher.

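### Functional performance in the joint-line objective has both a categorical and a numeric analysis, with no cut-point for the first and no rule for which one answers the objective

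*Combined protocol and SAP*

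**What the plan says.** **The objective.** Section 2.1.2 sets out to evaluate the effect of joint-line restoration, with "specific reference to effect on postoperative stability, anterior knee pain and functional performance at 2 and 5 years postoperatively". The last paragraph of section 1.1 repeats the three outcomes in the same order but names the measure of the third: "Stability, anterior knee pain and the functional component of the KSS will be evaluated with respect to JL".

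**The synopsis.** Under Statistical Methodology, Secondary, a t-test for independent groups or a nonparametric test is used to "compare the secondary numerical parameters (e.g. KSS, HSS, KOOS") between the joint-line subgroups at 1, 2 and 5 years. The same sentence then applies a Chi-square or Fisher's exact test "to compare the secondary categorical parameters (e.g. postoperative", and the list continues "stability, anterior knee pain and functional performance) between the" subgroups.

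**Section 9.**
- Section 9.1.2 includes "KSS pain and function score changes from preoperative at 1, 2 and 5-year visits" among the secondary efficacy parameters.
- Section 9.4.1 gives the KSS as its example of a continuous variable: "for continuous data (e.g. KSS) the N, mean, median, standard deviation, minimum and maximum will be computed".
- Section 9.1.5 assigns tests by type of variable. Numerical comparisons between subgroups get a paired t-test or Wilcoxon rank sum test, and categorical comparisons get Fisher's exact test. It allows a supportive ANCOVA of score change and sets the level: "A two-sided 0.05 alpha level will be used". It does not say which type functional performance is.

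**The concern.** The synopsis treats functional performance as a category. Section 1.1 treats it as a component of a numeric score, and section 9 handles that score numerically. A Chi-square or Fisher's exact test cannot be run on the KSS functional score until someone divides it into classes. The supplied text gives no classes, no responder level and no requirement to fix them before the data are seen.

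Two things are at stake. First, two results will exist for one of the three named outcomes of the joint-line objective, and they may disagree. The plan does not say which one counts. Second, the categorical result is the less efficient of the two, and its type I error is not controlled if the cut is chosen after looking. Section 1.1 limits the joint-line comparison to cases whose other knee was not replaced at the time of study surgery. The analysis set is therefore a subset of unstated size, with little precision to spare.

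**Working it through.** **1. How each place treats function in the joint-line comparison**

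| Place | Treatment |
|---|---|
| Synopsis, categorical list | category; Chi-square or Fisher's exact |
| Synopsis, numerical list | KSS named; independent t-test or nonparametric |
| Section 1.1 | functional component of the KSS |
| Section 9.1.2 | KSS function score, change from preoperative |
| Section 9.1.5 | test depends on type; function not classified |
| Section 9.4.1 | KSS is continuous |

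Only the categorical list in the synopsis points to a category. No entry ranks the two analyses.

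**2. The plan's own figure.** No sample size or power is given for the joint-line comparison. The primary figures reproduce: (35 × (1.645 + 0.842) / 7)² = 154.6 against the stated 154, and 154 / 0.85 = 181.2 against 181. They are used below only to set a scale: 154 evaluable cases cannot be exceeded by a subset of them.

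**3. Efficiency of the categorical test alone.** For a normal score cut so that a proportion q lies below, efficiency relative to the numeric comparison is φ(z_q)² / (q(1 − q)).
- q = 0.5: 0.3989² / 0.25 = 0.64
- q = 0.7: 0.3477² / 0.21 = 0.58
- q = 0.8: 0.2800² / 0.16 = 0.49
- q = 0.9: 0.1755² / 0.09 = 0.34

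**4. Power, if a cut were the only test.** Assumptions, since the documents give no effect, subset size, split or cut: normal score, difference 0.5 SD, two-sided 0.05, equal groups, cut at a percentile of the lower-scoring group. The numeric comparison needs 2 × (1.960 + 0.842)² / 0.5² = 62.8, so 63 per group for 80% power. For the categorical test, the two-proportion formula is used with p₁ = 1 − q and p₂ = 1 − Φ(z_q − 0.5). At the median this gives 0.500 against 0.691.

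| | Numeric | Cut at 50th | 70th | 80th | 90th |
|---|---|---|---|---|---|
| Per group for 80% power | 63 | 102 | 103 | 115 | 152 |
| Power, 77 vs 77 | 87% | 68% | 68% | 63% | 51% |
| Power, 77 in total | 59% | 40% | 40% | 37% | 29% |

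The 77 vs 77 row uses all 154 evaluable cases. The last row uses half of them.

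**5. Choosing the cut after the data are seen.** This simulation used 20,000 runs, no true difference and a nominal 5% level, with the most favourable cut reported.

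| Candidate cuts (percentiles) | Chi-square, 77 vs 77 | Fisher, 77 vs 77 | Chi-square, 38 vs 39 | Fisher, 38 vs 39 |
|---|---|---|---|---|
| 50 only | 4.4% | 3.1% | 4.2% | 3.7% |
| 30, 50, 70 | 11.3% | 7.6% | 11.9% | 9.2% |
| 20, 35, 50, 65, 80 | 17.0% | 11.6% | 16.9% | 12.9% |

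**The case against.** The strongest reply is that the numeric comparison is already planned. The synopsis sentence that contains the categorical list first compares KSS scores between the same joint-line groups. Section 9.1.2 keeps the function score change as a parameter, and section 9.1.5 permits an ANCOVA of it. A reader might infer from the categorical list that the plan throws away the numeric information. It does not, and that part of the reply stands. For the same reason, the power losses in step 4 describe a plan in which a cut replaces the numeric test, which is not what is written.

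The label is also only an example in a synopsis list. Read alone, sections 9.1.5 and 9.4.1 send the KSS function score to the numerical test, with no cut-point needed. This is fair, but it leaves the synopsis in conflict with section 9 and does not say which governs.

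A categorical function item may exist. Section 8.1 describes a postoperative functional evaluation that asks about any current impediment to function, and the case report forms and Appendix A are not in the supplied text. This cannot be excluded. If such an item is meant, the plan should name it, because section 1.1 names the KSS component.

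A reader might also infer that the categorical test would let a non-significant result pass as evidence that the group above 5 mm is no worse. That risk comes from section 2.1.2, which expects non-inferiority without giving a margin. It applies equally to a t-test and is not a consequence of this label.

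**Conclusion.** The inconsistency is real, and it is minor. One named outcome of a secondary objective is classed as categorical in the synopsis and measured by a numeric score elsewhere. No category is defined in the supplied text, and no rule says which analysis answers the objective.

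Taken alone, the categorical analysis carries about 64% of the information at a median cut and less at more extreme cuts, for a normal score. If the best of three to five cuts were reported, its type I error could reach about 11% to 17% with Chi-square, or 8% to 13% with Fisher's exact test. These figures rest on assumed normality and group sizes, and the simulated error rates also on the candidate cuts chosen. They show what is at risk if the categorical result is treated as the answer. They do not show that the plan as a whole loses this information, because the numeric comparison remains in it. The primary KSS conclusion is unaffected.

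**What to change.** 1. In the synopsis, remove functional performance from the examples of categorical parameters. Keep the categorical tests for outcomes that are recorded as categories.
2. In the synopsis and section 9.1.5, state that the functional-performance part of the joint-line objective is answered by the change in KSS functional score from preoperative to 2 and 5 years, the time points in section 2.1.2. Compare the groups with an independent-group t-test or Wilcoxon rank sum test.
3. In section 9.1.5, replace the paired t-test for between-subgroup comparisons. The joint-line groups contain different cases, so a paired test does not apply, and it conflicts with the independent-group test in the synopsis. Without this change, sending function to the numerical method would point to the wrong test.
4. If a coded categorical function item exists on the case report forms, name it, give its categories and label its comparison supportive.

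The cost is wording in two places. The evaluation schedule already collects the KSS preoperatively and at 2 and 5 years, so no new data are needed and no information is lost.

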#### CONFIDENTIAL

# **Evaluation Schedule**

Evaluation	Preoperative (4 months prior to surgery)	Intraoperative	6 weeks ( + 2 weeks)	6 months ( + 2 weeks)	1 year ( + 2 months)	2 years ( + 2 months)	5 years ( + 2 months)
Inclusion/ Exclusion	Х						
Demographics & Medical History	Х						
Preoperative KSS	Х						
Previous Implant Information		х					
Surgical Details		Х					
Postoperative KSS			х		х	х	х
SF-36	Х			Х	Х	Х	Х
KOOS	Х			Х	Х	Х	Х
Hospital for Special Surgery (HSS) Patella Score	х			х	х	х	х
LEAS	Х			Х	Х	Х	Х
Radiographs: Anteroposterior (AP), Mediolateral (ML) & Merchant (30° of flexion)	Х		Х		Х	Х	Х

KSS: The KSS is a subjective outcomes tool completed by the investigator that measures

function, pain, and motion.

SF-36: Short Form-36 (SF-36), is a 36 item patient questionnaire that evaluates general health and well being.

KOOS: The KOOS is a self-administered patient questionnaire that assesses pain, symptoms,

activities of daily living, sport and recreation function, and knee-related quality of life (QOL).

HSS Patella Score: The HSS Patella Score incorporates both subjective symptoms and objective data specific to the patellofemoral joint.

LEAS: The Lower Extremity Activity Scale (LEAS) is a self-administered patient evaluation designed to reflect patient activity.

### CONFIDENTIAL

## **1** Introduction

This document is a protocol for a human research study. This study will be conducted in compliance with the protocol, Good Clinical Practice (GCP) Standards, associated Federal regulations, and all applicable research requirements.

## 1.1 Background

As the population ages, so does the incidence of arthritis and subsequent primary TKR. Frequency of revision for failed TKR increases as well, aimed at alleviating pain and improving function following time-dependent primary implant failure or complications such as infection and fracture. The primary goals of revision TKR are to alleviate pain and provide the patient with stable, well-functioning TKR through optimal implant fixation and restoration of knee biomechanics. Appropriate TKR biomechanics are established through adequate flexionextension gap balancing, proper mechanical and rotational alignment, proper patellofemoral mechanics and restoration of the JL.

Revision TKR outcomes typically decline with each successive revision. However, patient expectations of postoperative function, pain relief and adequate QOL may not be adjusted for the expected decline in functional results observed in revision TKR. Some long-term data exists to describe the effectiveness of revision TKR. Sheng et al. performed a meta-analysis of publications on patient outcomes following revision TKR. Thirty-three studies with a total number of 1356 patients were included in this analysis, which reported increased function and motion compared to preoperative scores. The main indication for revision reported is aseptic loosening (55%). Other reasons include polyethylene wear (11%), instability (10%), infection (7%), progression of disease (4%), osteolysis (4%), bone fracture (4%), component failure (3%), stiffness (1%) and pain of unknown origin (1%). Instability can be caused by malposition of the JL, imbalance in flexion and extension gaps or incompetence of the posterior cruciate ligament.

There is little existing data reporting outcomes for a single type of revision TKR prosthesis, such as the Triathlon TS Total Knee System. To date, differences between various revision TKR implant systems are not reported in the scientific literature. Long-term outcomes data among a new generation of revision TKR prostheses is needed.

### CONFIDENTIAL

Page 8

In addition to improving patient outcomes, one of the challenges in revision TKR is restoration of the JL. Improper positioning of the JL has been shown to lead not only to instability but also to an increased incidence of anterior knee pain and decreased flexion. Malposition may also lead to patellar infera and posterior soft tissue impingement by the femoral component. Mason et al., in a study of six cadaver knees, investigated four anatomic landmarks for locating the JL during revision knee surgery – the medial femoral epicondyle (ME), the fibular head (FH), the tibial tubercle (TT), and the inferior pole of the patella (IPP). In this study, the distance between the ME and the JL showed very small patient-to-patient variability. As a result, it was concluded that the ME is a reliable and reproducible landmark for JL measurements.

Additionally, Mahoney and Kinsey retrospectively reviewed JL restoration and clinical outcomes in 22 consecutive femur revision cases. The authors used specialized instruments and were able to restore JL to within 2 mm of anatomic position in 12 of the 22 knees. Flexion and extension gap balancing and ME referencing were reliable methods of measuring and achieving proper position of the JL.

As a secondary objective, this outcomes study of the Triathlon TS Total Knee System will also examine the effect of JL restoration on a subset of revision TKR cases with a non-replaced contralateral knee at the time of study surgery. The effect will be evaluated by comparing between cases with JL restoration > 5 mm and cases with JL restoration  $\leq$  5 mm. As little as 5 mm of displacement from the JL can cause laxity in midflexion or tightness, even in a gap-balanced knee.

For all cases, at the time of study surgery, surgeons will intraoperatively measure, in millimeters, the distance between the ME and the JL in full extension and in 90° of flexion. This measurement will be taken before removal of the previous implants as well as after implantation of the final Triathlon® TS Total Knee System.

Additionally, preoperative and postoperative measurements of JL will be taken from AP radiographs, as the distance from the proximal tip of the FH to the distal most aspect of the femoral component. When the contralateral knee is non-replaced, the measurement will be taken on both sides. These additional measurements will be obtained during independent radiographic review to eliminate interobserver and intraobserver error.

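### Joint-line position is measured in millimetres but analysed only as a 5 mm split in a subset; add a supportive per-millimetre analysis beside the split

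*Combined protocol and SAP*

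**What the plan says.** **Measurement.** Section 1.1 says that for all cases "surgeons will intraoperatively measure, in millimeters, the distance between the ME and the JL in full extension and in 90° of flexion", before the old implants come out and after the new ones go in. An independent reviewer also measures from the fibular head to the femoral component on AP films. For those films, "When the contralateral knee is non-replaced, the measurement will be taken on both sides". Both measures are in millimetres or can be recorded so.

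**Analysis.** The JL effect is studied in "a subset of revision TKR cases with a non-replaced contralateral knee at the time of study surgery", and "The effect will be evaluated by comparing between cases with JL restoration > 5 mm and cases with JL restoration" of 5 mm or less. The Synopsis (Objectives and Statistical Methodology) uses the same two groups. Section 9.1.5 says "comparisons of numerical variables between subgroups (e.g. JL groups) will be made by a paired t-test or Wilcoxon rank sum test", with Fisher's exact test for categorical variables and "A two-sided 0.05 alpha level will be used" as the general rule. The optional ANCOVA there adjusts the subgroup comparison for covariates such as age, gender and BMI. It does not bring JL in as a continuous variable.

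**Expectation.** Section 2.1.2 expects that the "TS group with JL elevation > 5 mm is non-inferior to the Triathlon TS group with JL elevation" of 5 mm or less. No margin is given. Nor do the documents give the size of the subset, the expected share above 5 mm, or the power of this comparison.

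**The concern.** A cut at 5 mm treats a knee displaced by 0.5 mm and one displaced by 4.9 mm as the same, and knees at 4.9 and 5.1 mm as different, although measurement error alone can move a case across the line. If outcome worsens gradually with displacement, much of what was measured is lost.

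The secondary objective is the effect of JL position on stability, anterior knee pain and function. If few cases lie above the cut, the comparison can neither show an effect nor credibly exclude one. Because section 2.1.2 expects non-inferiority without a margin, while section 9.1.5 plans tests of difference, a non-significant result could be mistaken for support.

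**Working it through.** **1. The plan's own figure.** Section 9.4.2 uses SD 35, margin 7, one-sided alpha 0.05 and 80% power. Then n = (35 × (1.645 + 0.842) / 7)² = 154.6, against 154 stated. Allowing for 15% loss, 154 / 0.85 = 181.2, against 181 stated. Both reproduce. They concern the primary endpoint only.

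**2. Share above 5 mm.** The only accuracy figure is in section 1.1: "were able to restore JL to within 2 mm of anatomic position in 12 of the 22 knees", or 54.5% (exact 95% CI 32.2% to 75.6%). Assume displacement is normal with mean zero. Solving P(|Z| < z) = 12/22 gives z = 0.748, so SD = 2 / 0.748 = 2.67 mm and P(|d| > 5) = 6.2%. Other assumptions give:

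| Assumption | Share above 5 mm | Cases of 77 |
|---|---|---|
| Normal, 75.6% within 2 mm (SD 1.72) | 0.4% | 0.3 |
| Normal, 54.5% within 2 mm (SD 2.67) | 6.2% | 4.7 |
| Laplace, 54.5% within 2 mm | 14% | 11 |
| Normal, 32.2% within 2 mm (SD 4.82) | 30% | 23 |
| No shape assumed | 0 to 10/22 = 45% | 0 to 35 |

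The 77 is an assumption: half of the 154 evaluable cases have a non-replaced contralateral knee. Shares of 25%, 75% and 100% would give about 38, 115 and 154 cases. If only elevation counts, the shares under the centred normal model halve.

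**3. Detectable difference for the split.** With two-sided alpha 0.05, 80% power and SD 35 (total KSS change, a stand-in because no SD is given for the JL outcomes), the difference is 35 × (1.960 + 0.842) × √(1/a + 1/b) = 98.06 × √(1/a + 1/b).

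- 6%: 5 v 72 gives 45.3 points (46.5 with the unrounded 4.74 v 72.26)
- 30%: 23 v 54 gives 24.4 points
- 45%: 35 v 42 gives 22.4 points

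The best of these is about three times the plan's 7-point primary margin (22.4 / 7 = 3.2). At the 0.4% end there would be no group to compare.

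**4. Information kept by the split.** If the effect is linear in |d|, the fraction kept is the squared correlation between |d| and the indicator |d| > 5. It is about 39% at SD 2.67 mm, 64% at SD 4 mm and 68% at SD 5 mm.

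**5. What that means for power.** At SD 2.67 mm, |d| has SD 1.61 mm, and the two groups differ by 4.17 mm on average. For an assumed effect of 5 points per mm, power is Φ(5 × 1.61 × √n / 35 − 1.96) for the regression. For the split it is Φ(5 × 4.17 / (35 × √(1/a + 1/b)) − 1.96), with a = 0.0615n and b = n − a.

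- n = 77: 52% (mm) v 24% (split)
- n = 154: 82% (mm) v 43% (split)

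**The case against.** **A reader might infer that the protocol's own citation shows very few cases will exceed 5 mm.** It does not. The citation gives the share within 2 mm, not beyond 5 mm. The 6% needs a centred normal distribution and a point estimate from 22 knees operated on with specialized instruments. At an SD of 4 mm the share is 21%, or about 16 of 77, which is no handful.

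**A reader might also infer that an analysis in mm would bring in cases that the split leaves out.** It would not. The split already includes every case in the subset; it loses detail within the groups. Deviation from the patient's own anatomy needs the contralateral film, so the regression is confined to the same subset. The intraoperative before-and-after distance exists for everyone, but its change is relative to the previous implant.

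**The 5 mm cut has a stated clinical reason.** Section 1.1 cites 5 mm as enough displacement to cause laxity in midflexion or tightness. If the truth is a step at 5 mm, the same squared correlation works against the regression: a linear slope would keep only about 39% at SD 2.67 mm. This stands, and is why the regression should sit beside the split and not replace it.

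**The non-inferiority problem has its own source.** The missing margin in section 2.1.2 and the difference tests in section 9.1.5 would remain whatever the regressor. This also stands; the regression alone does not cure it.

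**Conclusion.** The point holds as a cheap improvement to a secondary analysis; it leaves the primary endpoint and its sample size untouched. JL is measured in mm, and every specified JL analysis discards all but which side of 5 mm a case falls on.

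If the effect is roughly linear in absolute displacement, the split keeps about 39% to 68% of the information over SDs of 2.67 to 5 mm. The comparison looks weak across the plausible range: about 45 points detectable at 6% above the cut, 22 to 24 points at 30% to 45%. These figures rest on the assumed subset of 77 and on the borrowed SD of 35. The share above the cut is unknown, and the documents do not support a firm claim that it is tiny. Appendix A, which holds the measurement protocol, was not in the text available, so the exact definition of displacement could not be checked.

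**What to change.** Keep the 5 mm comparison and add to section 9.1.5 a prespecified supportive analysis in the same subset:

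- Regress each outcome on JL displacement in mm: linear regression for scores, logistic regression for stability and anterior knee pain.
- Name the measurement that defines displacement. State that it is signed, with separate slopes for raised and lowered knees.
- Report the slope per mm and the predicted difference at 5 mm, each with a 95% CI.
- Report the number of cases above and below the cut, and state that a non-significant split is not evidence of non-inferiority.

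Defining the regressor requires reconciling JL restoration (Synopsis, section 1.1) with JL elevation (section 2.1.2). In the same edit, reconcile the paired t-test for separate groups in section 9.1.5 with the independent-group test in the Synopsis.

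**Cost.** A paragraph of text and a few tables, with no new data. The regression assumes a linear or two-slope relation, is less efficient than the split if the effect is a step at 5 mm, divides the subset further by direction, and remains limited to that subset.
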